### 7.2 Subject Disposition

Overall subject disposition for MIT-Do001-C302 study will be described in the SAP of the Efficacy Study part. This summary will also be produced for the Safety Study part based on the Included Set.

Data will be also summarized by hysterectomy status (hysterectomized and non-hysterectomized), including:

---

- Subjects in the Safety Study part (Included Set)
- Subjects treated
- Subjects who completed the treatment
- Subjects who discontinued treatment and reasons for discontinuation

The denominator for percentage of subjects treated will be the number of subjects allocated to the Safety Study part (Included Set). The denominator for subjects who completed or discontinued treatment will be the number of subjects treated in the Safety Study part (Safety Analysis Set).

A table summarizing the analysis sets will be presented by hysterectomy status (hysterectomized and non-hysterectomized) and overall for the Included Set, including:

- Subjects included in the Included Set
- Subjects in the Safety Analysis Set and reason for exclusion
- Subjects included in the PP Set and reasons for exclusion

In addition, a summary table of cumulative number of days from baseline for each visit will be provided.

A listing of subject disposition will be provided for the Included Set, with the extent of participation in the study and the reason for discontinuation. In addition, hysterectomy status will be flagged in the listing.

A listing of subjects included in each analysis set and reasons for exclusion will be provided for the Included Set.

### **7.3 Protocol Deviations**

A summary of major protocol deviations will be tabulated by type of deviation for the Safety Analysis Set.

All protocol deviations will be listed for the Included Set.

### **7.4 Demographics and Baseline Characteristics**

#### **7.4.1.1 Demographics**

Demographic data will be summarized using the Safety Analysis Set.

Continuous variables including age, body weight, height, BMI (at screening) will be summarized using descriptive statistics. Categorical variables including race, ethnic origin, and education level will be summarized using frequency counts and percentages.

Listings of demographics will be produced for the Included Set.

#### **7.4.1.2 Baseline Characteristics**

Subject baseline characteristics including hysterectomy status (hysterectomized and non-hysterectomized), smoking habits, gynecological history, PAP test, modified MENQOL questionnaire, Follicle Stimulating Hormone (FSH), Estradiol (E2) and Thyroid Stimulating

---

Hormone (TSH), lipid/glucose parameters (for inclusion), and the number of moderate to severe VMS per week during the Screening period.

Subject baseline characteristics will be summarized using the Safety Analysis Set. The summary will include descriptive statistics for continuous measures and frequency counts and percentages for categorical measures.

Tables summarizing subject baseline characteristics will also be presented by hysterectomy status (hysterectomized and non-hysterectomized).

Listings of baseline characteristics will be based on the Included Set.

#### 7.4.1.3 Medical History

A summary of medical history will be presented, by system organ class (SOC) and preferred term (PT) using Medical Dictionary for Regulatory Activities® (MedDRA) Version 24.1 or higher, for the Safety Analysis Set.

A listing including medical history and current medical conditions will be presented along with the SOC, PT by subjects for the Included Set.

#### 7.4.1.4 Prior and Concomitant Medications

Medications used in this study will be coded by using the latest available version of the World Health Organization (WHO) Drug Dictionary Enhanced (Enhanced 2019 March version, or higher).

**Prior medications:** A medication with a start date prior to Treatment Start Date.

**Concomitant medications:** A medication with a start date on or after Treatment Start Date.

If a medication start date is before the Treatment Start Date and is ongoing at Treatment Start Date, then the medication will be counted as both a prior and a concomitant medication.

Prior and concomitant medications will be summarized by anatomical therapeutic chemical (ATC) level 2 and preferred name (level 5) for the Safety Analysis Set. A listing of medication data will be produced for the Included Set.

Partial medication start and stop dates will be imputed as detailed in [Section 6.2.2](#).

### 7.5 Extent of Exposure

Treatment exposure (days) and compliance (%) of E4 will be assessed from study drug dispensing records. Descriptive statistics will be used to summarize duration of exposure and compliance of E4 for the Safety Analysis Set. Also compliance will be summarized categorically as the number of subjects with compliance < 80%, between 80% and 120% and > 120%.

Tables summarizing subject exposure to E4 will also be presented by hysterectomy status (hysterectomized and non-hysterectomized) for Safety Analysis Set.

A listing of study drug administration of E4 and P4, along with derived variables including duration of exposure, treatment compliance and compliance category, will be produced for the

---

Included Set.

## **7.6 Efficacy Analyses**

Descriptive statistics will be presented for efficacy endpoints. No formal statistical analyses are planned for evaluation of efficacy endpoints. The Safety Analysis Set will be the primary analysis set for the efficacy endpoints. The PP Set will be the sensitive analysis set for the efficacy endpoints.

### **7.6.1.1 Analysis Methods**

Not applicable

### **7.6.1.2 Multiplicity**

Not applicable

### **7.6.1.3 Treatment by Center Interaction Analysis (multi-center study)**

Not applicable

### **7.6.1.4 Analysis of Efficacy Endpoints**

### **7.6.1.5 Lipid and Glucose Metabolism**

Samples for lipid and glucose metabolism will be collected at Visit 1 (baseline), Visit 3 (week 12) and Visit 6 (EoT, week 52), including:

- Lipid metabolism: triglycerides, HDL-cholesterol, LDL-cholesterol, total cholesterol, lipoprotein(a) and total cholesterol/HDL-cholesterol ratio.
- Glucose metabolism: fasting glycemia, insulin, glycated hemoglobin and HOMA-IR.

The observed value and change from baseline to week 12 and week 52 for all parameters will be summarized using descriptive statistics including the number of subjects (n), mean, SD, median, min, and max and 95% CIs for the Safety Analysis Set and PP Set without imputation of missing data. In case of multiple measurement at the same visit, the last observed value will be used for the summary, regardless of scheduled or unscheduled. Visits will be clustered based on the windows specified in [Table 5](#) of Appendix 1.

Listings will be provided for lipid and glucose metabolism data for the Included Set.

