Washout periods are: 1 week for vaginal hormonal products (rings, creams, gels); 4 weeks for transdermal estrogen or estrogen/progestin products; 8 weeks for oral estrogen and/or progestin and/or selective estrogen receptor modulator therapy; 8 weeks for intrauterine progestin therapy; 3 months for progestin implants or estrogen alone injectable drug therapy; 6 months for estrogen pellet therapy or progestin injectable drug therapy; 8 weeks for oral, topical, vaginal, patch of androgen/DHEA; 6 months for implantable or injectable androgen therapy; 2 weeks for phytoestrogens or black cohosh, 3 months for venlafaxine and desvenlafaxine if used for the treatment of VMS and 4 weeks all other non-hormonal prescription or over-the-counter treatments used for VMS.
- b) Every effort needs to be made to perform the procedures of the end of trial visit for those subjects that discontinue their participation.
- c) Visits will be scheduled in one of the seven days of week 5, week 13, week 29, week 41, and week 53 thus allowing a visit window of 7 days. Unscheduled visits may be needed during the treatment period for additional unforeseen safety assessments.
- d) At Washout visit and Screening visit only available I/E criteria at that time point will be checked.
- e) Blood pressure, heart rate, body height (during screening only) and body weight (during screening and EoT only).
- f) To be performed in subjects with uterus and/or cervix, unless a written normal result is available within 18 months before screening start. The PAP test may be repeated once in case of inadequate or insufficient sample.
- g) Unless a written normal result, including digital imaging, is available within 9 months before screening start.
- h) Mammography at EoT visit may only be performed if the subject was treated for at least 12 weeks and the last mammography was taken at least 9 months earlier
- i) If the subject is not fasting, a new appointment needs to be made as soon as possible. Laboratory tests may be repeated once during the screening period, at the discretion of the investigator.
- j) Additional blood samples, including one DNA sample at Visit 1 only, will be collected for optional additional analysis of in the context of this program or any further research on E4.
- k) A pregnancy test may be performed at the discretion of the Investigator.

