9.6.3. COVID-19 vaccination

Subjects cannot be excluded from the trial based on vaccination status for COVID-19 consistent with restriction for other vaccinations, which may happen in the subjects (influenza, tetanus and other).

Subjects can be vaccinated with a regulatory approved COVID-19 vaccine according to national guidelines but should not participate in a COVID-19 clinical trial.

Recommendation on the timing of the COVID-19 vaccination in relation to study assessments, due to possible acute reaction on vaccination:

- The vaccination should be performed preferably after regular visits with the planned blood collections.
- Otherwise minimum one week before regular visits with blood samples collections.

Rationale for timing restriction: the acute reaction on vaccination may cause transitory changes in biochemistry (liver enzymes, LDH etc.), it is not a common reaction but may happen. The possible transitory increase in temperature may cause changes in absorption of study drug, PK fluctuations etc.

In case of any acute condition, the scheduled visit should be postponed (if no safety issues) until the status of the subject improves.

The vaccination during the trial should be reported as concomitant medication. Any AE that occurs after vaccination should be properly reported.

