## 7 STATISTICAL METHODS

### 7.1 General Statistical Conventions

All statistical procedures will be completed using SAS version 9.4 or higher, there is only one treatment group, thus no formal statistical analysis will be performed.

Confidence intervals (CIs) will be presented as 2-sided 95% CIs unless specified differently in specific analysis.

Categorical variables will be summarized using frequency counts (n) and percentages in each category, percentages will be computed for subjects with non-missing value (as the denominator). If there are missing values, missing values counts will be provided. All percentages will be rounded to one digit after decimal point. The frequency counts and percentages will be presented in the form XX (XX.X %), where the percentage is in the parentheses. If the percentage of a category is '100 %', then it will be displayed as '100 %' (no decimals will be added after 100).

Continuous variables will be summarized using the number of subjects with non-missing values (n), mean, median, standard deviation (SD), minimum (min), maximum (max) and missing values counts. Missing values counts will be displayed only if there are missing values. All mean and median values will be formatted to one more decimal place than the measured value. Standard deviations will be formatted to two more decimal places than the measured value. The min and max will be displayed to the same number of decimal places as the measured value. Unscheduled visits will not be summarized in tables.

Analyses will be performed by visit, irrespective of any time window deviations, unless otherwise specified. The early discontinuation (ED) visit will be separated from the scheduled EoT- visit based on discontinuation reason. Unscheduled visits related to efficacy data will be clustered with scheduled visits based on the visit windows in [Table 5](#) of Appendix 1. Similarly, the unscheduled visit results will be clustered with scheduled visits based on the visit windows defined in [Table 6](#) (Appendix 1) for microscopic findings and laboratory endpoints and endometrial biopsy. Similarly, the scheduled visits for ECG, Procedures, Questionnaire, Vital Signs, Imaging and Findings will be based on visit window [Table 7](#) in Appendix 1.

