#### 7.6.1.6.2 Analysis of Menopause-Specific Quality of Life

The observed value and change from baseline to week 12 and week 52 for MENQOL total score and scores for each domain (vasomotor, psychosocial, physical, and sexual functioning) will be summarized by using descriptive statistics including number of subjects (n), mean, SD, median, min, and max and 95% CIs for the Safety Analysis Set and PP Analysis Set. Visits

---

will be clustered as specified in [Table 5](#) of Appendix 1.

A listing will be provided for MENQOL questionnaire data for the Included Set.

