## 10 APPENDICES

### Appendix 1 Visit Schedule and Permitted Time Window:

**Table 5: Visit Window for Efficacy Analysis of Safety Study part**

Assessment Visit	Time window	Visit
Washout visit	n.a.	Week - 12 to week -4 
Screening period	n.a.	Week - 4 to week - 1 
Visit 1	n.a.	Week 1
Visit 2	Day 29 - 35	Week 4
Visit 3	Day 85 - 91	Week 12
Visit 4	Day 197 - 203	Week 28
Visit 5	Day 281 - 287	Week 40
Visit 6	Day 365 - 371	Week 52
Visit 7 NH subjects only	Day 379 - 392	Week 55/56

: The week numbers for the Washout visit and Screening period may deviate. The washout visit is generally up to 8 weeks prior to the screening visit. The Screening period is up to 4 weeks, but may be extended to a maximum of 6 weeks.

n.a.: not applicable

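### SAP Table 5 gives efficacy data only 7-day windows: an unscheduled fasting redraw outside them has no visit, and late scheduled visits and MENQOL are left to two possible programming rules

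*SAP*

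**What the plan says.** - **Lipid and glucose (SAP 7.6.1.5).** Samples are scheduled at Visits 1, 3 and 6. Observed values and changes at Week 12 and Week 52 are summarised descriptively with 95% CIs. For repeats: "In case of multiple measurement at the same visit, the last observed value will be used for the summary, regardless of scheduled or unscheduled". The next sentence reads "Visits will be clustered based on the windows specified in" Table 5 of Appendix 1.
- **MENQOL (SAP 7.6.1.6.2).** Visits "will be clustered as specified in" Table 5.
- **Table 5**, titled "Visit Window for Efficacy Analysis of Safety Study part", gives Day 85-91 for Visit 3 (Week 12) and Day 365-371 for Visit 6 (Week 52). It has no rule for the days between windows and no early-discontinuation row.
- **General rule (SAP 7.1).** "Analyses will be performed by visit, irrespective of any time window deviations, unless otherwise specified". Unscheduled efficacy visits go to Table 5, unscheduled laboratory endpoints and biopsies go to Table 6, and unscheduled visits as such are kept out of the tables. Also, "the scheduled visits for ECG, Procedures, Questionnaire, Vital Signs, Imaging and Findings will be based on visit window" Table 7, which lists visits with no day ranges.
- **Protocol 2.2, footnote i**, on fasted blood samples: "If the subject is not fasting, a new appointment needs to be made as soon as possible".
- **Protocol 9.6.3**: "In case of any acute condition, the scheduled visit should be postponed (if no safety issues) until the status of the subject improves".

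**The concern.** A scheduling window tells a site when to book a visit. An analysis window has to give a place to every measurement that was actually taken. Table 5 uses the first as the second. Three things follow.

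1. An unscheduled efficacy value outside a 7-day window cannot be clustered, so it stays unscheduled and is left out of the summary tables. This defeats the stated intention to use values whether scheduled or not.
2. The Table 5 sentences in 7.6.1.5 and 7.6.1.6.2 are not limited to unscheduled visits. They can be read as an exception to the nominal-visit rule in 7.1, so that a late scheduled visit loses its place as well.
3. MENQOL has two assignment rules.

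Two programmers following the SAP could therefore report different numbers of women, means and CIs at Week 12 and Week 52 from the same data. In an open-label single arm, that choice would be made with the data in view.

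**Working it through.** **Reproducing the windows.** Study week w runs from day 7(w-1)+1 to day 7w. Week 13 is 7×12+1 = 85 to 91, and Week 53 is 7×52+1 = 365 to 371. Each has 7 days, as in protocol Table 4 and footnote c of protocol 2.2. SAP Table 5 has the same day ranges under the labels Week 12 and Week 52.

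**What Table 5 leaves out.** The five on-treatment windows cover 5×7 = 35 of the 370 days from Day 2 to Day 371, so 335 (90.5%) have no visit. Adding Visit 7 (Day 379-392, 14 days) gives 49 of 391 days, so 342 (87.5%) have none. The gaps that matter are those around the two analysis visits:
- around Week 12: Day 36-84 (49 days) and Day 92-196 (105 days);
- around Week 52: Day 288-364 (77 days) and Day 372-378 (7 days).

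**Room for a redraw.** A Visit 3 on Day 85 leaves 91-85 = 6 days for a redraw inside the window. A Visit 3 on Day 91, equally compliant, leaves none.

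**Unscheduled lipid or glucose redraw, by table:**

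| Day of redraw | Table 5 | Table 6 ranges |
|---|---|---|
| 90 | Week 12 | Week 13 |
| 95 | no visit | Week 13 (75-144) |
| 373 | no visit | Week 53 |
| 380, non-hysterectomized | Visit 7 follow-up | Week 55/56 follow-up (376 onward) |
| 380, hysterectomized | no applicable row | Week 53 (327 onward) |

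Table 6 accepts 70 days for Week 13 (75-144, 63 more than Table 5). For Week 53 in non-hysterectomized women it accepts 50 days (326-375, 43 more).

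**Scheduled Visit 6 on Day 373.** Under the nominal rule in 7.1 it is Week 52. If 7.6.1.5 counts as otherwise specified, it has no visit. The SAP does not say which applies.

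**MENQOL.** SAP 7.6.1.6.2 names Table 5; 7.1 puts questionnaires under Table 7. Dividing the tables into efficacy and safety does not settle this. The on-treatment questionnaires in this part are MENQOL and CGI, and SAP 2.2 makes both efficacy endpoints. For CGI, 7.6.1.7 names no table. The labels also differ: Week 12 and 52 in Table 5, Week 13 and 53 in Tables 6 and 7.

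**The case against.** The strongest reply is that 7.1 already protects scheduled visits. It analyses by visit whatever the day and sends only unscheduled efficacy data to Table 5. The Table 5 sentence in 7.6.1.5 uses the same verb and follows directly on the rule for repeat values, so it can be read as covering repeats only. A visit postponed under protocol 9.6.3 is still a scheduled visit. This stands: a reader might infer that late Visit 3 or Visit 6 results are certainly excluded, but the documents support only that they may be.

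Further points that stand:
- A reader might infer that Table 6 contradicts Table 5 for lipid and glucose. SAP 7.7 ties Tables 6 and 7 to safety endpoints, and the day ranges in Table 6 apply only to unscheduled visits, so a split by endpoint type is a fair reading.
- The 90.5% and 87.5% figures describe the table, not the data lost. Post-baseline lipid, glucose and MENQOL data are scheduled only at Visits 3 and 6, so most of those days should hold none.
- A redraw inside the same window is kept by the last-value rule.
- Early-discontinuation visits are already separated from the end-of-treatment visit in 7.1. Table 5 merely lacks the row.
- Under protocol 10.1.6.6 the last E4 dose is taken the evening before Visit 6, and non-hysterectomized women then start P4. A redraw after Visit 6 is normally off E4 and is not a plain Week 52 value.

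None of this gives a visit to the unscheduled Day 95 redraw or settles the MENQOL rule.

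**Conclusion.** The point holds for unscheduled values. As written, a fasting lipid or glucose redraw recorded as unscheduled and taken outside Day 85-91 or Day 365-371 does not reach the Week 12 or Week 52 summary. It would still appear in the listings. For late scheduled visits and for MENQOL the defect is an unresolved choice between two rules, not a stated exclusion.

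The size cannot be given. The documents contain no rate of late visits or redraws, and any count of women would rest on an invented one. A reader might also infer that the loss is informative because illness or non-compliance causes it. That is possible, but nothing in the documents shows it.

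The endpoints are secondary, in one arm, with no formal test, so no primary conclusion is at risk. It is still worth correcting before database lock: the rule works against the SAP's own intention, and the remedy is already largely in the SAP.

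**What to change.** 1. In SAP 7.1, 7.6.1.5 and 7.6.1.6.2, state that scheduled Visits 2, 3 and 6 are assigned by nominal visit irrespective of day.
2. Cluster unscheduled lipid and glucose values with the ranges already in Table 6: Day 75-144 for Week 12; for Week 52, Day 326-375 (non-hysterectomized) or Day 327 onward (hysterectomized). Keep the last-observed-value rule.
3. Flag, or show in a sensitivity summary, any value taken after the last E4 dose or after P4 has started.
4. Name one table for MENQOL and CGI, and use one set of week labels.
5. Show early-discontinuation efficacy values in their own row, consistent with 7.1 and Tables 6 and 7.

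The cost is a few sentences and one programming rule. The downside is a wider spread of actual days: Day 144 lies in study week 21 (Day 141-147) and would count as Week 12. The SAP already accepts that spread for its unscheduled safety laboratory data.

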### **7.6.1.6 Menopause-Specific Quality of Life Questionnaire**

#### **7.6.1.6.1 Scoring Rule of Menopause-Specific Quality of Life**

The MENQOL is a 29 item (Q1-Q29) assessment of quality of life designed to capture self-reported information on the presence and bother of symptoms, feelings and experiences in the domains of vasomotor, psychosocial, physical, and sexual functioning, among midlife women

in immediate post-menopause period. Table 2 provides the list of the relevant numbered items for each domain.

**Table 2: Items numbers for each domain**

Domains	Items numbers
Vasomotor	1 to 3
Psychosocial	4 to 10
Physical	11 to 26
Sexual functioning	27 to 29

At baseline women complete the modified MENQOL questionnaire, responding for symptoms over the previous 3 days. During the study women complete the MENQOL questionnaire, answering about symptoms over the previous 1-month period.

For each item, women will be asked to report if they experience that symptom or feeling, and if they do, to rate how much it bothered them on a scale of 0–6 corresponding to ‘not at all bothered’ to ‘extremely bothered’. Non-endorsement of an item will be scored a ‘1’ and endorsement a ‘2’, plus the number of the particular rating, so that the possible score on any item ranges from 1 (not experiencing symptoms or feeling) to 8 (extremely bothered), as described in Table 3.

**Table 3: Scoring of each Items**

Experienced that symptom or feeling?	No	Yes						
		2						
Endorsement	1	0	1	2	3	4	5	6
Rating		0	1	2	3	4	5	6
Score	1	2	3	4	5	6	7	8

Each domain score is the mean of the non-missing item scores in that domain (higher scores indicated poorer quality of life) if at least 50% of the items within a domain function have been rated, as described in [Section 6.2.1](#).

Overall MENQOL total score is the mean of the non-missing domain scores, if at least 50% of the domains have a score, as described in [Section 6.2.1](#).

